DCR is defined as the proportion of subjects who have BOR of CR or PR or SD (duration from C1D1 to SD has to be ≥ 7 weeks).
CBR is defined as the proportion of subjects who have BOR of CR or PR or durable SD (duration of SD ≥ 23 weeks).
PFS is defined as the time from the first study dose date to the date of first documentation of disease progression or death (whichever occurs first) (Part 2 only).

TTP is defined as the time from the first study dose date to the date of first documentation of disease progression (Part 2 only).

DOR is defined as the time from the first documentation of CR or PR to the date of first documentation of disease progression or death (whichever occurs first) (Part 2 only).

TTR is defined as the time from the date of first study dose to the date of first documentation of CR or PR. (Part 2 only).

OS is defined as the time from the date of first study dose to the date of death from any cause. Subjects who are lost to follow-up and the subjects who are alive at the date of data cutoff will be censored at the date the subject was last known alive or the cut-off date, whichever comes earlier (Part 2 only).

Analysis Sets

DLT Analysis Set will include all subjects (Part 1 only) who have completed Cycle 1 without major protocol deviation with at least 75% of lenvatinib compliance and at least 2 doses of nivolumab and are assessed for DLT, and subjects who have experienced DLT during Cycle 1. This will be the analysis set to determine tolerability.

Safety Analysis Set will include all subjects who received at least 1 dose of lenvatinib or nivolumab.

PK Analysis Set will include all subjects who have received at least 1 dose of lenvatinib and nivolumab, and have evaluable concentration data.

The Efficacy Analysis Set will include all subjects who received at least 1 dose of lenvatinib and nivolumab.

The Pharmacodynamic and PGx Analysis Set is the group of subjects who received at least 1 dose of lenvatinib and nivolumab and had at least 1 postdose pharmacodynamic or PGx data.

Efficacy Analyses

Efficacy analyses will be conducted by part based on the Efficacy Analysis Set. Tumor assessment will be analyzed based on the investigator's assessment. If needed, the analysis based on independent review will be conducted.

Part 1: BOR will be summarized, and ORR and their corresponding exact 2-sided 95% confidence interval (CI) will be calculated. DCR and CBR will be summarized in a same manner.

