9.1.3.3 Follow-up Phase

The Follow-up Phase will consist of the examination at study discontinuation and the last observation visit which occurs 30 days after final administration of study drug. The subject who discontinues study will have a discontinuation visit and last observation which occurs 30 days after final administration of study drug. If a new anticancer agent needs to be immediately started due to deterioration in the subject’s condition, the final observation visit can be conducted before 30 days after the last dose of the study drug has passed but prior to starting a new anticancer agent. If the last observation visit occurs within 7 days after study drug discontinuation, discontinuation data can be used as the last observation data.

In Part 2, all subjects will be followed for survival until death every 12 weeks (± 2 week) from the date of discontinuation, except where a subject withdraws consent or the sponsor chooses to halt survival follow-up. The survival follow-up will be continued until discontinuation of the last subject or for up to 2 years after Cycle 1 Day 1 of the last subject enrolled in Part 2, whichever occurs later.

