4 DETERMINATION OF SAMPLE SIZE

A sample size of approximately 26 subjects will be enrolled in this study, 6 subjects for Part 1 and 20 patients for Part 2. Six subjects in Part 1 was deemed appropriate to evaluate the tolerability of the dose and perform preliminary safety assessment. Twenty subjects in Part 2 was determined to further evaluate the safety and preliminary efficacy. The probability to detect at least 1 development of intolerable treatment-related AEs with a true incidence of 10%, 15% or 20% in 20 subjects was 87.8%, 96.1%, or 98.8%, respectively. Therefore, the sample size is determined to be approximately 20 subjects.

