TTR (months) = (Date of documentation of CR or PR – Date of first dose + 1) / (365.25/12).

OS is defined as the time from the date of first study dose to the date of death due to any cause and calculated as below. Subjects who are lost to follow-up and the subjects who are alive at the date of data cutoff will be censored at the date the subject was last known alive or the cut-off date, whichever comes earlier. Censoring rules for OS are shown in [Table 3](#)
Censoring rules for OS. OS will also be summarized in the same manner as with PFS.

OS (months) = (Date of death/ censored date – Date of first dose + 1) / (365.25/12).

A waterfall plot will be presented for the percent changes from baseline in the sum of the diameters of target lesions at post-baseline nadir (ie, maximum tumor shrinkage). A spider plot will be presented for the percent changes from baseline in the sum of the diameters of target lesions. The diameters after subsequent anti-cancer treatment initiation are not included in the waterfall and spider plot.

Summary statistics for tumor marker (AFP) the changes and percent changes from baseline will be presented by visit. Also, AFP will be categorized as >200 µg/L or <= 200 µg/L and presented by visit.

Subject data listings will be provided.

Table 1 Censoring rules for PFS

No.	Situation	Date of Event or Censoring	Outcome
1	No baseline tumor assessments	Date of first dose	Censored
2	Progression documented at scheduled visit	Date of first radiologic PD assessment	Event
3	Progression documented between scheduled visits	Date of first radiologic PD assessment	Event
4	No progression nor death at the time of data cut-off or discontinuation from study treatment	Date of last adequate radiologic assessment*	Censored
5	New anticancer treatment started	Date of last adequate radiologic assessment* prior to or on date of new anticancer treatment	Censored
6	Death before first PD assessment	Date of death	Event
7	Death between adequate assessment visits*	Date of death	Event
8	Death or progression after two or more consecutive missed visit/tumor assessment**	Date of last adequate radiologic assessment* before missed tumor assessments	Censored

* Adequate tumor assessment is a radiologic assessment of CR, PR, SD, non-CR/non-PD or PD as determined by investigators.

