* Adequate tumor assessment is a radiologic assessment of CR, PR, SD, non-CR/non-PD or PD as determined by investigators.

** More than one missed visit is defined if the duration between the last tumor assessment and PD is longer than 126 days (ie. 8 weeks x 2 + 2 weeks [allowance of visit]) for subjects on the every 8 week scanning schedule in this study.

The priority of the censoring rules is as follows:

1. If the subject had PD, the following sequence will be applied:

- If a subject did not have baseline tumor assessment (No. 1), the subject will be censored on date of first dose.
- If a subject had new anticancer treatment before PD (No. 5), the subject will be censored on the date of the last adequate tumor assessment prior to or on the date of new anticancer treatment.
- If a subject missed two or more assessments consecutively before PD (No. 8), the subject will be censored on the date of the last adequate tumor assessment before PD.
- Otherwise, if a subject had an event (No. 2, 3), the earliest event date will be used.

2. If a subject did not have PD, the censoring date will be the earliest censoring date if the subject met multiple censoring criteria (No. 1, 4, 5, 6, 7, 8).

Table 3 Censoring rules for OS

No.	Situation	Date of Event or Censoring	Outcome
1	Death before or on data cut off	Date of Death	Event
2	Death after data cut off	Date of data cut off	Censored
3	Subject still alive at data cut off	Date of data cut off	Censored
4	Subject lost to follow-up or withdraw of consent before data cut off	Date last known to be alive	Censored

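### SAP Table 3 and the OS text give different censoring dates for some subjects alive at cut-off; the wording should be aligned, and the effect on OS is small and conditional

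*SAP*

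**What the plan says.** **OS text, SAP 5.4.1.** Subjects lost to follow-up and subjects alive at the cut-off form one group, which "will be censored at the date the subject was last known alive or the cut-off date, whichever comes earlier". The protocol synopsis (Study Endpoints) gives the same rule for Part 2. The SAP text then refers to Table 3 for the censoring rules.

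**SAP Table 3.** Row 3, "Subject still alive at data cut off", is censored at the date of data cut-off. The last-known-alive date appears only in row 4, "Subject lost to follow-up or withdraw of consent before data cut off". Tables 1 and 2 (PFS and TTP) each carry a priority list for overlapping rules. Table 3 has none.

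**Follow-up.** Under protocol 9.1.3.3, in Part 2 "all subjects will be followed for survival until death every 12 weeks", with a window of ±2 weeks, counted from discontinuation. Neither document states whether survival status is checked at the cut-off.

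**Use of the date.** The censoring date enters the endpoint directly: "OS (months) = (Date of death/ censored date", minus first-dose date, plus 1, converted to months. The method is Kaplan-Meier, since "OS will also be summarized in the same manner as with PFS".

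**The concern.** Take a subject who has stopped treatment, is still in survival follow-up, and was last reached some weeks before the cut-off. This subject is neither lost nor withdrawn, so row 4 does not apply, and row 3 is the only row that seems to fit. Row 3 gives the cut-off date; the text gives the earlier contact date. The same SAP therefore supports two OS datasets from the same records, and the table departs from the protocol.

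The choice matters because time after the last contact is time in which a death may have happened without yet being recorded. Counting it keeps the subject in the risk set while any such death is missing from the event count, and that raises the Kaplan-Meier estimate late in the curve.

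**Working it through.** **1. The plan's own figures.** No design figure is given for OS. The only one in the plan concerns adverse events in Part 2: "in 20 subjects was 87.8%, 96.1%, or 98.8%, respectively". With 1 − (1 − p)^20 at p = 0.10, 0.15 and 0.20, the results are 87.84%, 96.12% and 98.85%, so the stated figures reproduce. They fix n = 20 for Part 2 and say nothing about OS precision.

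**2. Which subjects get two dates**

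| Subject | OS text | Table 3 | Same date? |
|---|---|---|---|
| Died after cut-off | cut-off | cut-off (row 2) | yes |
| Confirmed alive on or after cut-off | cut-off | cut-off (row 3) | yes |
| Lost or withdrawn before cut-off | last known alive | last known alive (row 4) | yes |
| In survival follow-up, last contact before cut-off | last contact | cut-off (row 3 as worded) | **no** |

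**3. Size of the gap for one subject.** One month is 365.25/12 = 30.4375 days.
- Contact exactly 12 weeks before cut-off: 84/30.4375 = 2.76 months.
- Interval stretched by the 2-week window, 14 weeks: 98/30.4375 = 3.22 months.
- Successive contacts at opposite window limits, 12 + 2 + 2 = 16 weeks: 112/30.4375 = 3.68 months.

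Subjects on treatment are seen on Days 1 and 15 of each cycle, so their gap is about 2 weeks.

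**4. Effect on the curve, 24-month minimum follow-up.** The documents give no OS, accrual or contact-timing figures, so these are assumptions: exponential OS, 12-month accrual, last contact uniform over 0 to 12 weeks before cut-off, n = 20, 2,000 simulated trials per row. *Verified* means status known for all subjects to cut-off. In the Table 3 and text columns, deaths after last contact are unknown. *Mixed* means deaths are known to cut-off but survivors are censored at last contact. Entries are mean Kaplan-Meier OS in percent.

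| Median OS (months) | Time | Verified | Table 3 | Text | Mixed | Table 3 − text |
|---|---|---|---|---|---|---|
| 12 | 24 mo | 24.79 | 24.94 | 24.78 | 24.64 | +0.16 |
| 18 | 24 mo | 39.67 | 39.85 | 39.69 | 39.52 | +0.16 |
| 24 | 24 mo | 50.12 | 50.30 | 50.16 | 49.98 | +0.14 |
| 36 | 24 mo | 62.87 | 62.99 | 62.85 | 62.73 | +0.14 |
| 12 | 30 mo | 17.37 | 18.51 | 17.51 | 16.35 | +1.00 |
| 18 | 30 mo | 31.48 | 32.83 | 31.43 | 30.03 | +1.40 |
| 24 | 30 mo | 42.38 | 43.56 | 42.24 | 40.99 | +1.32 |
| 36 | 30 mo | 56.02 | 57.24 | 56.08 | 54.73 | +1.16 |

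At 24 months few subjects are yet near their censoring time and the rules barely differ. At 30 months, inside the censoring range, Table 3 is 1.0 to 1.4 points above the text rule. In the mixed case the text rule falls 1.0 to 1.45 points below the verified result (17.37 − 16.35 = 1.02; 31.48 − 30.03 = 1.45).

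**5. Effect with an earlier cut-off.** Here the assumptions are median treatment of 7 months, median OS of 12 to 24 months, contacts every 12 weeks after discontinuation, no status check at cut-off, n = 20 and 4,000 trials per scenario. With cut-off 6 to 12 months after the last entry, the Table 3 bias at 12 to 18 months is about +1.4 to +2 points, and the text rule stays within about 0.3 points of the verified curve. Over these and the 24-month scenario, roughly 5 to 15 subject-months are unverified and 0.3 to 0.6 deaths per trial are hidden.

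**The case against.** The strongest reply is that the plan already contains the right rule. The OS text states it in full and matches the protocol, so only the table is at fault. Row 2, on death after cut-off, can be applied only if some status information from after the cut-off is available. Beside it, row 3 can be read as *known to be alive at cut-off*, and for such subjects the two rules coincide. The programming specifications are separate documents, and the SAP says that data handling is settled before database lock, so nobody can tell from these documents which rule will be coded.

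This stands in part. It shows that the difference may never materialise. It does not rescue the table: row 3 does not say *confirmed*, and if it did, subjects last contacted before cut-off would have no row.

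A reader might go further and infer that reported OS will be inflated. The documents do not support that. It requires that deaths after last contact be unknown and that no status check be made at cut-off, and the documents are silent on both. If deaths are ascertained to cut-off while survivors are censored at last contact, the text rule is the biased one, downward and by a similar amount. Nor should the shift of nearly 2 points be taken as the expected size, because it needs an assumed early cut-off. Protocol 9.7 allows a data cut-off for a primary analysis but gives no date, and survival follow-up is planned to at least 2 years after the last Part 2 subject starts, unless the sponsor halts it.

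**Conclusion.** The contradiction is certain and lies in current text: Table 3 row 3 conflicts with the OS text in the same section and with the protocol. Its numerical effect is conditional and small: about +0.1 to +0.2 points at 24 months with a 24-month cut-off, and about 1 to 2 points in the censored tail or with an earlier cut-off. Those sizes rest on assumed accrual, treatment duration, OS and contact timing, with later deaths unknown and no status check at cut-off.

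The point is minor. OS is a descriptive Part 2 endpoint in about 20 subjects, it is not among the listed primary or secondary endpoints, and no statistical comparison is planned. For scale, a survival estimate near 50% with n = 20 has an approximate 95% half-width of 1.96 × √(0.25/20) = 0.219, or 22 points. No conclusion would turn on the shift. The reason to act is that one dataset should not yield two OS results under one plan.

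**What to change.** Change the date in Table 3 row 3 to *date last known to be alive or date of data cut off, whichever is earlier*. Subjects confirmed alive on or after cut-off are still censored at the cut-off.

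That edit alone does not settle the direction of bias. The SAP should also state whether survival status is checked at cut-off, and should apply the same vital-status cut-off to deaths and survivors, so that deaths are not counted up to a later date than the one to which survivors are known to be alive.

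The cost is one cell of wording and a sentence on status checking. OS may come out slightly less favourable than under row 3 as written.

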5.5 Pharmacokinetic, Pharmacodynamic, Pharmacogenomic, and Other Biomarker Analyses

5.5.1 Pharmacokinetic Analyses

The Safety Analysis Set will be used for individual lenvatinib plasma concentrations and nivolumab serum concentrations listings. The PK Analysis Set will be used for the summaries of lenvatinib plasma concentrations and nivolumab serum concentrations, for summaries and listings of PK parameters of lenvatinib. The PK Analysis Set for lenvatinib and for nivolumab will be used for each analysis.

5.5.1.1 Plasma or serum Concentration and its PK Parameter Analysis

<Concentration>

Plasma concentration values for lenvatinib and serum concentration values for nivolumab will be summarized by dose level using summary statistics (n, mean, standard deviation [SD], median, minimum [min] and maximum [max]) by Part and nominal time point.

Plasma concentrations of lenvatinib, serum concentrations of nivolumab will be listed for each subject by actual sampling time.

<PK Parameter (Lenvatinib only in Part 1)>

PK parameters will be derived by non-compartmental analysis using WinNonlin software (version 6.2.1 or later) according to 302-104.01-MNL.

The following pharmacokinetic parameters for lenvatinib will be calculated: C_{max} , t_{max} , $AUC_{(0-t)}$, $AUC_{(0-inf)}$, $t_{1/2}$, λ_z , CL/F , V_z/F , MRT , $C_{ss,max}$, $C_{ss,min}$, $t_{ss,max}$, $AUC_{(0-t)}$, CL_{ss}/F , $C_{ss,av}$, $R_{ac}(C_{max})$, $R_{ac}(AUC)$, and PTF ratio.

$R_{ac}(AUC)$ will be calculated based on $AUC_{(0-t)}$ not $AUC_{(0-t)}$ of Cycle Day 1 and Cycle Day 15.

Other PK parameters may be calculated as appropriate.

Summary statistics will be tabulated for the PK parameters of lenvatinib by dose level. Summary statistics (n, mean, SD, median, min, and max) will be presented for all parameters (apart from t_{max} and $t_{ss,max}$ where mean and SD are not required). In addition, geometric mean and %CV will also be presented for all parameters apart from t_{max} and $t_{ss,max}$.

PK parameters of lenvatinib for each subject will be listed.

5.5.1.2 Pharmacokinetic Data Figures

The linear and semi-log plots of plasma concentration for lenvatinib versus actual time will be displayed by individual subjects in Part 1. The actual time will be plotted on the X axis and the concentrations of lenvatinib will be plotted by dose level on the Y axis. The linear and semi-

log mean (+SD) plots of lenvatinib plasma concentration versus nominal time will be displayed in Part 1. The nominal time will be plotted on the X axis and the mean (+SD) will be plotted by dose level on the Y axis on the same graph by visit (Cycle 1 Day 1 and Cycle1 Day 15).

The linear plots of individual and mean (\pm SD) pre-dose serum concentration for nivolumab will be displayed by Part. For plots of individual concentrations, actual time will be used. For plot of mean concentrations, the nominal time will be used.

The linear mean (\pm SD) plots of nivolumab pre-dose serum concentration versus nominal time will be displayed by Part. The nominal time will be plotted on the X axis and the mean (\pm SD) will be plotted on the Y axis.

5.5.2 Pharmacodynamic, Pharmacogenomic, and Other Biomarker Analyses

The effect of lenvatinib-nivolumab combination therapy on soluble and/or tissue biomarkers will be summarized using descriptive statistics. This analysis will be performed only when relevant biomarkers are evaluated and the analysis is deemed necessary.

5.6 Safety Analyses

All DLT analyses will be performed on the DLT Analysis Set. All other safety analyses will be performed on the Safety Analysis Set by part. Safety data will be summarized using descriptive statistics (eg, n, mean, standard deviation, median, minimum, maximum for continuous variables; n [%] for categorical variables).

5.6.1 Extent of Exposure

The parameters to be summarized are defined as follows.

These parameters for extent of exposure will be computed and presented for lenvatinib alone and nivolumab alone, separately.

For lenvatinib:

- Number of cycles = The last cycle with at least one lenvatinib dosing
- Duration of treatment (days) = Last dosing date – first dosing date + 1
- Duration of treatment (months) = (Last dosing date – first dosing date + 1) / (365.25/12)
- Number of subject-month with study drug dosing = Sum of duration of treatment (months) per subjects
- Total number of doses = Sum of days with lenvatinib dosing
- Total doses (mg) = Sum of all the actual dose
- Dose intensity (mg / days) = Total doses / Duration of treatment (days)
- Relative dose intensity (%) = $100 \times \text{Dose intensity} / \text{planned starting dose (8 or 12 mg)}$

For nivolumab:

- Number of cycles = The last cycle with at least one nivolumab dosing
- Duration of treatment (days) = Last dosing date with nivolumab – first dosing date + 1
- Duration of treatment (months) = (Last dosing date with nivolumab – first dosing date + 1) / (365.25/12)
- Number of subject-month with study drug dosing = Sum of duration of treatment (months) per subjects
- Total number of doses = Sum of days with nivolumab dosing
- Total doses (mg) = Sum of all the actual dose derived by [240 (mg) x (Actual volume infused (ml) / volume to be infused (ml))]
- Dose intensity (mg / 2weeks) = Total doses / ((Last dosing date with nivolumab – first dosing date + 14) / 14)
- Relative dose intensity (%) = $100 \times \text{Dose intensity} / 240 \text{ (mg)}$

Number of cycles as combination therapy of lenvatinib and nivolumab will also be calculated and presented. The smaller number of cycles within a subject is defined as the number of cycle as combination therapy.

Furthermore, the following information of administration will also be summarized for both lenvatinib and nivolumab based on study medication data.

For lenvatinib, the number (percentage) of subjects who experienced a dose reduction and interruption will be summarized. For subjects who experienced a dose reduction, cycle of the first dose reduction will be summarized by descriptive statistics. Cycle of the first dose interruption will also be summarized in subjects who experienced a dose interruption. Frequency of dose reductions will be summarized by categories (1, 2, 3, ≥ 4). Frequency of dose interruptions will also be summarized by appropriate categories (e.g., 1, 2, 3, ≥ 4).

The date of dose reduction (from XX mg to YY mg, $XX > YY > 0$) is defined as the first date of planned dose of 0 mg followed by YY mg. The first date of 0 mg has to follow planned dose of XX mg. If the starting dose of YY mg does not follow 0 mg but XX mg, the first date of planned dose of YY mg is regarded as the date of dose reduction. Note that from 4 mg QD to 4mg QOD is also dose reduction.

The dose interruption is defined as the case where planned dose is 0 mg. The starting date of dose interruption is defined as the first date of planned dose of 0 mg following and followed by same dose level (> 0 mg). For example: 12 mg followed by 0 mg and followed by 12 mg; 8 mg followed by 0 mg followed by 8 mg. Successive days with planned dose of 0 mg is counted as one dose interruption event. If after dose 0 mg, the subject discontinued from lenvatinib permanently, it is not regarded as a drug interruption (but as a drug discontinuation).

An illustration for dose reduction and interruption in a subject is shown in Figure 2.

[figure not shown]

Figure 2 Dose reduction and interruption for lenvatinib

For nivolumab, the number (percentage) of subjects who experienced a dose interruption will be summarized. Cycle of first dose interruption will be summarized by descriptive statistics in subjects who experienced a dose interruption. Frequency of dose interruptions will be summarized by appropriate categories (e.g., 1, 2, 3, ≥ 4).

The dose interruption is defined as the case where planned dose of 0 mg. Successive dates with planned dose of 0 mg is counted as one dose interruption event, and the first date with

planned dose of 0 mg is defined as the starting date of dose interruption. If after dose 0 mg, the subject discontinued from nivolumab permanently, it is not regarded as a drug interruption (but as a drug discontinuation).

Subject data listings will be provided.

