9.4.1.2 Nivolumab

Nivolumab injection for intravenous infusion contains 100 mg/10 mL of nivolumab in each vial. Nivolumab will be administered at a dose of 240 mg as an IV infusion over 30 minutes, Q2W (Day 1 and Day 15 of each cycle). Please refer to the current version of the Investigator's Brochure (IB) and instructions for handling of investigational products for complete storage, preparation and administration information for nivolumab.

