Pulmonary toxicity, diarrhea, or colitis	Grade \geq 2	Baseline
Others	Grade \geq 2	Grade \leq 1 or baseline value (Endocrinopathies adequately controlled with only physiologic hormone replacement may resume treatment.)

ULN: upper limit of normal.

a: A delay of nivolumab for more than 6 weeks will require sponsor's approval before treatment can be resumed.

9.4.1.3.2.2.2 Discontinuation Criteria of Nivolumab

Nivolumab treatment should be discontinued for the following AEs related to nivolumab:

- Any Grade 2 uveitis, eye pain or blurred vision that does not respond to topical therapy and does not improve to Grade 1 severity within the re-treatment period or requires systemic treatment.
- Any Grade 3 uveitis, pneumonitis, bronchospasm, hypersensitivity reaction, or infusion reaction.
- Any Grade 3 thrombocytopenia lasting >7 days or associated with bleeding.
- Any Grade 3 AE lasting >7 days, with the exceptions of skin, laboratory abnormalities, endocrinopathies adequately controlled with only physiologic hormone replacement.
- Any hepatotoxicity as below:

- AST or ALT $>10 \times \text{ULN}$ for >2 weeks
- AST or ALT $>15 \times \text{ULN}$
- For subjects with total bilirubin $\leq \text{ULN}$ at baseline: total bilirubin $>5 \times \text{ULN}$
- For subjects with increased bilirubin at baseline: total bilirubin $>8 \times \text{ULN}$
- Any Grade 4 AE or laboratory abnormality, except for the following
 - Neutropenia <7 days
 - Lymphopenia or leukopenia
 - Amylase or lipase abnormalities that are not associated with symptoms or clinical manifestations of pancreatitis.
 - Isolated electrolyte imbalances/abnormalities that are not associated with clinical sequelae and are corrected with supplementation/appropriate management within 72 hours of their onset.
 - Endocrinopathy adverse events that are adequately controlled with physiologic hormone replacement.

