3.2.3.2 Treatment Period

In the Treatment Period, subjects will receive lenvatinib in combination with nivolumab. The Treatment Period will begin with the first dose of study drug administration on Cycle 1

Day 1. Each cycle is 28 days long and subjects continue treatment until they meet any of the criteria in “Discontinuation Criteria by Subject (see [Protocol Section 9.3.3.1](#))”.

Subjects will be hospitalized during the Cycle 1, however, outpatient is allowed after Cycle 1 Day 15, when investigator or subinvestigator judges that that the subject’s safety is ensured.

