Calculation of creatinine clearance

To calculate a creatinine clearance (mL/min), the Cockcroft & Cault formula will be used.

Males: $((140 - \text{age (years)}) \times \text{weight (kg)}) / (\text{Creatinine (serum:mg/dL}) \times 72)$

Females: $((140 - \text{age (years)}) \times \text{weight (kg)} \times 0.85) / (\text{Creatinine (serum:mg/dL}) \times 72)$

Visit Windows

The purpose of visit windows is to provide a single record per subject per visit for the calculation of descriptive statistics for safety parameters (e.g., laboratory values and vital signs, etc.) per scheduled visit, and change from baseline per visit. Other safety analyses (e.g., worst grade laboratory results) will include all observations.

The observation closest to the target date will be used in by visit summaries. If two or more observations have the same distance to the target visit day, the one that has the highest CTCAE grade or is furthest away from the normal range will be used for summary tables. If

the multiple data in the same distance to the target date are in the same range from normal value, the data measured at an earlier date will be used for summary tables.

The visit window is applied for safety assessment item which is scheduled at each visit.

Analysis visit	Target Day	Visit Window	
		Start Day of Visit Window	End Day of Visit Window
Cycle 1 Day 8	Cycle 1 Day 1 + 7	Cycle 1 Day 1 + 5	Cycle 1 Day 1 + 9
Cycle 1 Day 15	Cycle 1 Day 1 + 14	Cycle 1 Day 1 + 12	Cycle 1 Day 1 + 16
Cycle 1 Day 22	Cycle 1 Day 1 + 21	Cycle 1 Day 1 + 19	Cycle 1 Day 1 + 23
Cycle 2 Day 1	Cycle 1 Day 1 + 28	Cycle 1 Day 1 + 28	Cycle 1 Day 1 + 31
Cycle 2 Day 8	Cycle 1 Day 1 + 35	Cycle 1 Day 1 + 32	Cycle 1 Day 1 + 38
Cycle 2 Day 15	Cycle 1 Day 1 + 42	Cycle 1 Day 1 + 39	Cycle 1 Day 1 + 45
Cycle 2 Day 22	Cycle 1 Day 1 + 49	Cycle 1 Day 1 + 46	Cycle 1 Day 1 + 52
Cycle n Day 1 ($n \geq 3$)	Cycle 1 Day 1 + 28 x (n-1)	Cycle 1 Day 1 + 28 x (n-1) - 3	Cycle 1 Day 1 + 28 x (n-1) + 3
Cycle n Day 8 ($n \geq 3$)	Cycle 1 Day 1 + 28 x (n-1) + 7	Cycle 1 Day 1 + 28 x (n-1) + 4	Cycle 1 Day 1 + 28 x (n-1) + 10
Cycle n Day 15 ($n \geq 3$)	Cycle 1 Day 1 + 28 x (n-1) + 14	Cycle 1 Day 1 + 28 x (n-1) + 11	Cycle 1 Day 1 + 28 x (n-1) + 17
Cycle n Day 22 ($n \geq 3$)	Cycle 1 Day 1 + 28 x (n-1) + 21	Cycle 1 Day 1 + 28 x (n-1) + 18	Cycle 1 Day 1 + 28 x (n-1) + 24
End of Treatment	30 days after last dose	Date of last dose	Date of last dose + 37

C1D1 is the day of first dosing.

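### SAP 5.6.1 takes the smaller of the two drugs' last dosed cycle numbers as the number of combination cycles, so a cycle in which one drug was wholly skipped and later resumed still counts as combination therapy

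*SAP*

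**What the plan says.** SAP 5.6.1 (Extent of Exposure) gives parallel definitions for the two drugs. For lenvatinib: "Number of cycles = The last cycle with at least one lenvatinib dosing". For nivolumab: "Number of cycles = The last cycle with at least one nivolumab dosing". Each is the number of the last dosed cycle, not a count of dosed cycles. A combination figure is then derived: "The smaller number of cycles within a subject is defined as the number of cycle as combination therapy". Both versions of the SAP in the file carry the same rule.

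On timing, SAP 3.2.3.2 states: "Each cycle is 28 days long". Protocol 9.4.1.2 puts nivolumab on Days 1 and 15 of each cycle. Protocol 9.4.1.3.2 allows the dosing of either drug, or of both, to be modified. Two limits apply to holds:

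- Nivolumab (Protocol Table 4, footnote a): "A delay of nivolumab for more than 6 weeks will require sponsor's approval before treatment can be resumed".
- Lenvatinib (Protocol Table 2, footnote a): an interruption of more than 28 days for treatment-related toxicity must be discussed with the sponsor before restarting.

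One drug may therefore be held while the other continues, and the held drug may later be resumed.

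**The concern.** A line headed as cycles of combination therapy will be read as the number of cycles in which subjects received both drugs. The rule does not deliver that. It takes the smaller of two end points and treats every cycle up to it as combination therapy, including any in which one drug was not given at all.

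The primary objective is the tolerability and safety of the combination, and this is the only exposure summary in SAP 5.6.1 that describes the two drugs together. The groups are small: 6 subjects in Part 1 and 20 in Part 2, each also shown by 8 mg and 12 mg lenvatinib group. What is at stake is the accuracy of one descriptive exposure figure. The dose decision does not depend on it.

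**Working it through.** The plan states no value for combination cycles, so there is no figure of its own to reproduce. The check compares the rule with a direct count.

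**Formulas.** Let L and N be the sets of cycles with at least one dose of lenvatinib and of nivolumab.

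- SAP figure = min(max L, max N).
- Cycles with both drugs = the number of cycles in both L and N.

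**Direction.** Every cycle in both sets is numbered no higher than min(max L, max N), so the direct count cannot exceed the SAP figure. As a check, all 32 × 32 = 1,024 dosing patterns over six cycles, with both drugs started in Cycle 1, were enumerated. The SAP figure was never below the direct count. It was equal in 120 patterns and higher in the other 904, by at most 4 cycles. These are possible patterns, not expected frequencies.

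**Hypothetical subjects.**

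| Dosing | SAP figure | Cycles with both drugs |
|---|---|---|
| Six cycles, none wholly skipped | 6 | 6 |
| Six cycles, nivolumab absent throughout Cycle 3 | 6 | 5 |
| Six cycles, lenvatinib absent in Cycle 2 and nivolumab in Cycle 4 | 6 | 4 |
| Lenvatinib Cycles 1–6, nivolumab stopped for good after Cycle 3 | 3 | 3 |
| Lenvatinib Cycles 1–12, nivolumab Cycles 1, 2, 6, 7, 8 | min(12, 8) = 8 | 5 |

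**Can a whole nivolumab cycle be missed without sponsor approval?** Assume cycle numbers follow the 28-day calendar, and count days from Day 1 of cycle k as day 0. The last infusion is on Day 15 of cycle k (day 14). Both infusions of cycle k+1 are missed, and the next is on Day 1 of cycle k+2 (day 56).

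- Interval between infusions: 56 − 14 = 42 days.
- Delay past the due date (day 28): 56 − 28 = 28 days.

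On either way of measuring delay, this is not more than 6 weeks.

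**Size for such a subject.** One cycle too many is 1/10 = 10% of a reported figure of 10 and 1/6 = 16.7% of a reported figure of 6. In the last row of the table the excess is 8 − 5 = 3 cycles, or 3/5 = 60% above the direct count. That row needs a hold from the infusion due on Cycle 3 Day 1 to Cycle 6 Day 1, which is 3 × 28 = 84 days or 12 weeks, so sponsor approval would be required.

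**Lenvatinib.** A 28-day interruption empties a whole cycle only if it starts on Day 1. Otherwise both adjoining cycles contain doses. Longer interruptions are possible after discussion with the sponsor.

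**The case against.** The strongest reply is that nothing depends on this number. Part 1 tolerability is decided by DLTs in Cycle 1, in a set that already requires adequate dosing of both drugs or a DLT. Adverse events are summarized per subject, not per combination cycle, and no comparison is planned. Protocol 9.7.1.8.1 asks only for exposure to each drug separately, so the combination line is an addition. This stands, and it limits the weight of the point.

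Next, holds show elsewhere in the same section. In the 8-versus-5 illustration, if nivolumab is last given on Cycle 8 Day 15 there are 10 infusions over (210 + 14)/14 = 16 two-week intervals, so relative dose intensity is 10/16 = 62.5%. This stands in part. The per-drug figures show that nivolumab was missed, but not in how many cycles the two drugs were given together. Interruption counts help less: consecutive zero-dose days form one event whatever their length, and a lenvatinib hold followed by a lower dose is classed as a reduction.

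It can also be said that the rule matches the section's convention, since duration of treatment likewise runs through holds. That is fair as a defence of a last-cycle-reached measure, but not of calling it cycles of combination therapy.

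Three stronger readings might be inferred, and the documents do not support them:

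- That every 6-week nivolumab delay empties exactly one cycle. The protocol does not define how delay is measured. If it is the interval between infusions, Cycle 4 Day 1 to Cycle 5 Day 15 is 42 days and empties none.
- That the SAP fixes cycle numbers to the calendar for exposure. Section 8.3 uses that numbering for safety visit windows only, and no text says how cycles are numbered when dosing is delayed.
- That the least tolerant subjects are the ones overstated. Subjects who stop one drug for good are handled correctly; the error needs a wholly skipped cycle followed by resumption.

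**Conclusion.** The definition does not measure what its label says, and any error it makes is upward. It errs only for a subject who misses a whole cycle of one drug and resumes that drug at or before the smaller last cycle. For nivolumab, one such missed cycle can occur without sponsor approval and adds one cycle to that subject's figure; longer approved holds add more.

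The sizes given are for an affected subject and rest on calendar numbering of cycles, which is plausible but not stated for exposure. The documents give no frequency of such holds, so the effect on the trial summary cannot be stated. The correction is worth making because the reported figure can be wrong and putting it right costs little. Nothing here calls the DLT assessment or the tolerability conclusion into question.

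**What to change.** In SAP 5.6.1, define the number of cycles of combination therapy as the count of cycles with at least one lenvatinib dose and at least one nivolumab dose. If the present figure is wanted, keep it as a separate line labelled as the last cycle reached on both drugs. One sentence on how cycles are numbered when dosing is delayed would remove the remaining ambiguity.

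The cost is a small derivation change using dosing data already collected, and the reported number of combination cycles may fall slightly. The new count is still a low bar, since a cycle with one lenvatinib day and one infusion would qualify, so it should be read beside the per-drug dose intensities.
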